## **6. BIOSTATISTICAL ANALYSIS**

**EEG acquisition Preprocessing:** Continuous 64-channel EEG will be recorded. All data will be stored for subsequent off-line analysis. We will apply an anti-aliasing filter and down-sample the EEG data to reduce computational complexity before analysis. Bandpass filtering of the acquired signal will vary depending upon

the features of the EEG data of interest. Trigger signals will be sent from the stimulus delivery system to the EEG recording system to tag the stimulus events for subsequent binning, temporal epoching and averaging of EEG data into the relevant evoked potential averages.

**Spectral Analysis:** We will compute spectrograms for all subjects using the multitaper method. We will also compute group-level baseline-normalized spectrograms for induction and emergence by taking the median across subjects with the data aligned to the LOC and ROC time points, respectively. To assess statistical significance for the difference in EEG spectra at each frequency, we will compute the 99% confidence interval of the median difference between groups by using an empirical bootstrap approach. The null hypothesis will be rejected only if the confidence interval of the median difference at each frequency exceeds the significance threshold over a contiguous frequency range  $\geq 2W$ .

**Eigenvalue and Modal Projection Analyses:** We will perform an eigenvector decomposition analysis of the cross-spectral matrix to identify the principal modes of oscillation in the conscious and unconscious states and to analyze how activity within these principal modes changes through time. We will estimate the cross-spectral matrices  $P_{\text{baseline}}(f)$  and  $P_{\text{unconscious}}(f)$  at each frequency  $f$  using the multitaper method using data from the full baseline period, as well as segments of at least 5 min extending from LOC to ROC, respectively, for each subject. An eigenvalue decomposition of the median cross-spectral matrix at each frequency will be performed. Each eigenvector describes a coherent spatial distribution or mode of oscillation, and the corresponding eigenvalue quantifies the power in this mode. We then use modal projection analysis to characterize how power within principal modes change as a function of time. A permutation-based procedure will be performed to assess statistical significance for the modal projection analysis.

**Behavioral Analysis:** The probability of response to verbal stimuli and the difference in probability of response will be estimated by using Bayesian Monte Carlo methods to fit a state-space model to these data. To perform group-level analyses, we will align the behavioral data across subjects with respect to each subject's LOC time for induction and with respect to each subject's ROC time for emergence. We will then pool the responses, and pooled data will be used to estimate group-level probabilities of response using the state-space model.

**Inflammatory profile Analysis:** Plasma samples will be submitted to Myriad/Rules Based Medicine (Myriad RBM, Austin, TX, USA) for analysis using their proprietary platform. Wilcoxon rank-sum tests with corrections for multiple comparisons will be used to assess analyte differences. In exploratory analyses, we will examine Pearson correlations between analytes and variables of interest (i.e. pain, anxiety).

**Power Analysis:** Assuming the point estimate for gamma power at baseline is -20 dB and 5 dB for ketamine induced-unconsciousness (**Fig 2.**), a standard deviation of 20 dB, type 1 error of 0.05, and desired power of 0.9,  $n=14$  study volunteers will enable us to detect a gamma power ratio of 25 dB. Therefore, we aim to recruit up to 15 subjects.

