### Ketamine

Ketamine is an anesthetic, an anesthetic adjunct and an analgesic that acts primarily by binding to NMDA type glutamate receptors in the brain and spinal cord. Ketamine is a channel blocker and thus requires an open channel to be effective. Because the channels on inhibitory interneurons are generally more active than those on pyramidal neurons, ketamine primarily affects inhibitory interneurons at low to moderate doses (Fig. 1), leading typically to increased neural activity. This is why cerebral metabolism increases with low doses of ketamine. Hallucinations, dissociative states, euphoria and dysphoria are common with low dose ketamine because brain regions, such as the cortex, hippocampus and amygdala, continue to communicate

but with less modulation and control by inhibitory interneurons. Information is processed without proper coordination in space and time. This state is associated with high frequency beta-gamma (>30 Hz) oscillations. Analgesia results most likely from the action of ketamine on glutamate NMDA receptors at the dorsal root ganglia, the first synapse of the pain pathway in the spinal cord where glutamate is the primary neurotransmitter (Fig. 1).

We analyzed 4-channel frontal EEG recorded during routine monitoring in patients receiving ketamine (2mg/kg; n = 12 patients) to induce general anesthesia for surgery. As illustrated in figure 2 (middle panel), immediately after induction, we observed an alternating pattern of slow oscillations (0.1-4 Hz) and gamma bursts (30-40 Hz). Also illustrated in figure 2 (right most panel), this oscillatory dynamic eventually transitioned to persistent gamma oscillations (30-40 Hz) after several minutes. Both the slow-gamma and gamma patterns were associated with increased theta oscillations (4-8 Hz) and decreased beta/gamma oscillations (10-20 Hz).

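### The 99% bootstrap interval for the EEG spectra is not assured to be 99% at 14 or 15 subjects, because the estimand, resampling unit and interval type are left open

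*Combined protocol and SAP*

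**What the plan says.** The Spectral Analysis paragraph of Section 6 first describes a within-subject summary: "We will also compute group-level baseline-normalized spectrograms for induction and emergence by taking the median across subjects". It then gives its test of spectral differences at each frequency: "we will compute the 99% confidence interval of the median difference between groups by using an empirical bootstrap approach". The null is rejected only if the interval "exceeds the significance threshold over a contiguous frequency range" of at least 2W.

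The design is a single cohort. Section 4 marks randomization as not applicable, and the Power Analysis says "we aim to recruit up to 15 subjects". The eigenvalue analysis in the same section takes baseline data and "segments of at least 5 min extending from LOC to ROC, respectively, for each subject", so both states are recorded in each person.

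The protocol does not define the two groups, the resampling unit, the type of bootstrap interval, the number of resamples, W, the frequency range or the threshold.

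**The concern.** With 14 or 15 subjects the bootstrap distribution of a median sits on a few ordered values, so a nominal 99% interval can have quite different real coverage. The result depends on choices the text leaves open. Two analysts following it faithfully could print intervals labelled 99% that miss the true value well over 1% of the time, or intervals so wide that a large effect is often not detected. This interval is the only test the plan states for differences in the spectra at each frequency, so those claims carry whatever error it has.

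**Working it through.** **Inputs.** From Section 6: nominal level 99%; n=14 (powered) and 15 (maximum); a shift of 25 dB (from -20 to 5 dB); and "a standard deviation of 20 dB, type 1 error of 0.05, and desired power of 0.9". Assumed, because not given: normal data, SD 20 dB in each state, between-state correlation (0.5 for the power figures, 0 to 0.8 for coverage), and a threshold of 0 dB.

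**The plan's own figure.** 2 × [20 × (1.960 + 1.282) / 25]² = 13.45, which rounds up to 14. So n=14 reproduces with the two-sided normal formula for two independent groups, read per group.

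**Reading A: median of each subject's difference, percentile limits.**
- At n=15, the bootstrap median is at or below the j-th ordered difference with probability P(Bin(15, j/15) ≥ 8). This is 0.0042 for j=3 and 0.0255 for j=4. The 0.5% point therefore falls on the 4th value and, by symmetry, the 99.5% point on the 12th.
- Coverage of the 4th to 12th is 1 − 2 × P(Bin(15, 0.5) ≤ 3) = 96.48% for any continuous distribution, an error of 3.5%. That is the limit for unlimited resamples. With 1,000 resamples, simulated error is about 2.5% to 3%.
- At n=14, using the exact weights of the 7th and 8th resample positions, error is 2.2% to 2.3% for normal, heavy-tailed and skewed differences, and about 2% with finite resamples.

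**Reading A, basic limits** (reflected about the sample median; normal differences). Error is about 10% to 11% at n=14 and 12% to 14% at n=15 with finite resamples (15% in the limit).

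**Reading B: difference of the two state medians, percentile limits.**
- Whole subjects resampled: coverage 99.2% to 99.9% over correlations 0 to 0.8, at both sample sizes.
- States resampled separately: coverage 99.1% to 100%.
- Power for 25 dB at n=15 and correlation 0.5: about 51% to 54% with separate resampling, against about 73% to 75% with whole subjects (range over repeated simulations). At correlation 0 the two are equal, at 52%.
- Basic limits on this statistic with whole subjects resampled cover only 90% to 94%.

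**Exact alternative for Reading A.** The interval from the k-th smallest to the k-th largest difference covers 1 − 2 × P(Bin(n, 0.5) ≤ k−1):

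| n | Ordered differences | Coverage |
|---|---|---|
| 15 | 3rd to 13th | 99.26% |
| 14 | 2nd to 13th | 99.82% |
| 14 | 3rd to 12th | 98.71% |

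**Its power per frequency.** At correlation 0.5 the SD of a difference is 20 × √(2 × 0.5) = 20 dB, so a difference is positive with probability Φ(25/20) = 0.894. The opposite tail is negligible.
- n=15, 3rd to 13th: P(Bin(15, 0.894) ≥ 13) = 0.274 + 0.332 + 0.187 = 79%, against about 90% for percentile limits.
- n=14, 2nd to 13th: P(Bin(14, 0.894) ≥ 13) = 0.346 + 0.209 = 56%, against about 89% for percentile limits.
- n=14, 3rd to 12th: 0.266 + 0.346 + 0.209 = 82%.

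**The case against.** The strongest reply is that a shortfall in coverage is not a property of the written plan. The plan names neither estimand nor interval type, and one legitimate paired analysis, the percentile interval for the difference of state medians with whole subjects resampled, is close to 99%. This stands. The 96.48% figure is conditional on Reading A, percentile limits and very many resamples, and is not a finding about what will be done.

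Second, even 96.5% to 98% per frequency is stricter than the 0.05 in the Power Analysis, and requiring a run of at least 2W can only make rejection harder. Both are true. But the 0.05 belongs to one gamma comparison, whereas the spectral paragraph promises 99% at each frequency, and an interval printed as 99% should be one.

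A reader might go further and infer that the 2W rule lets through a known, high rate of false bands. The documents do not support that: any such rate needs W, the frequency range, the smoothness of the spectra and the threshold, and none is given.

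A reader might also infer from the between-groups wording, and from n=14 matching an independent-groups formula, that pairing will be discarded. That is not shown either. The preceding sentence uses baseline-normalized data and a median across subjects, which points to a within-subject analysis, and a sample-size formula does not settle how the data will be resampled.

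**Conclusion.** The stated 99% is not assured at n=14 or 15. On the within-subject median, the likelier reading, standard bootstrap limits err about 2 to 3.5 times as often as stated (percentile) or about 10 to 14 times (basic, normal differences). On the difference of state medians, percentile limits are near nominal if subjects stay intact and needlessly wide if they do not; the loss is roughly 20 points of power at an assumed correlation of 0.5, SD 20 dB and normal data.

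The consequence is limited to the spectral comparisons. The effect on the 2W rule cannot be quantified from the documents. The point is worth correcting before analysis, because it is cheap and removes both the false label and the possible loss of power.

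**What to change.** In the Spectral Analysis paragraph of Section 6:

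1. Replace the between-groups estimand with the median of each subject's dB difference between two named states.
2. Keep each subject's two states together in any resampling.
3. Use the exact order-statistic interval and print its actual coverage: n=15, 3rd to 13th (99.26%); n=14, 2nd to 13th (99.82%), or 3rd to 12th labelled 98.71%.
4. If the bootstrap is kept instead, resample whole subjects, state the interval type and number of resamples, and print the true coverage in place of 99%.
5. Keep the 2W rule, and state W, the frequency range and the threshold (0 dB, if that is what is meant).

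The authors' median-based approach can stay; no mean-based replacement test is needed.

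The cost is a few sentences and a little code, with no new data. Intervals become somewhat wider, and per-frequency power for 25 dB at assumed correlation 0.5 falls from about 90% to 79% at n=15, and from about 89% to 56% at n=14 with the 2nd to 13th interval (82% with the 3rd to 12th). Part of that lost power was bought by error above the stated 1%.

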During this period, a calibrated cuff pain stimuli will be delivered to the gastrocnemius area of the lower leg using a validated cuff pain device (Hokanson Rapid Cuff Inflator), titrated to 8-9/10 pain. One advantage of using cuff algometry pain is that, unlike more superficial methods (e.g. heat pain), cuff pain responses are unaffected by sensitization or desensitization of the skin. The following questionnaires will be administered to assess pain intensity and quality: 1) PROMIS Numeric Rating Scale V1.0 – Pain Intensity 1A; 2) PROMIS Scale v2.0 – Neuropathic Pain Quality 5a; and, 3) PROMIS Scale v2.0 – Nociceptive Pain Quality 5a. Participants will be oriented to the following pain scale: (1) 0-1 out of 10 as “tolerable”; (2) 2-3 out of 10 as “slight discomfort”; (3) 4-7 out of 10 as “moderate discomfort”; (4) 8-9 out of 10 as “painful”; and (5) 10 as “maximum pain”.

**B. Baseline:** A 10 to 15-minute period of EEG recording will be obtained for EEG calibration (i.e. eye movements, eye blinks, facial muscle movement) and EEG normalization (awake-eyes closed). Recordings of physiological measurements (blood pressure, heart rate, pulse oximetry, end-tidal carbon dioxide, electrooculogram, electromyogram and galvanic skin response) will be initiated and maintained from the beginning of the study protocol until the subject is ready for discharge.

**C. Loss consciousness:** 2mg/kg of ketamine will be infused (Medfusion pump) over approximately 5 minutes to gradually induce and allow for rapid emergence from ketamine-anesthesia. This anesthetic dose is expected to cause approximately 10-15 minutes of loss of consciousness/responsiveness. Subjects will be asked to respond to auditory stimuli via button-press jittered at random between 4 and 8 second intervals in order to resolve the precise period at which loss and recovery of consciousness/responsiveness occurred at a fine temporal scale.

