General anesthetic agents, including ketamine, can produce apnea after loss of consciousness. The standard clinical approach for airway management in surgical patients is for the anesthesiologist to assist oxygenation and ventilation after the loss of consciousness. Thus, a staff anesthesiologist will use standard airway maneuvers to maintain normal oxygenation and ventilation. These maneuvers include a jaw and chin thrust and assisted ventilation with a mask and bag as part of a circle circuit. Ventilation will be manually assisted as needed. At all times, the inspired oxygen concentration, expired carbon dioxide waveform and partial pressure will be monitored continuously. The minimum inspired oxygen concentration will be 30%. The end-tidal (capnogram) carbon dioxide levels will be maintained within 10% of the baseline values. Manually assisted oxygenation and ventilation will continue until the subject recovers spontaneous ventilation. Vlisides et al. recently studied correlates of ketamine-anesthesia. Because the authors rapidly administered 1.5mg/kg bolus of ketamine, the temporal correlation of EEG dynamics with loss of consciousness was not feasible in this study. Also, this study did not relate ketamine-induced altered arousal states to pain perception. While planning the present study, we spoke with the study authors and confirmed that spontaneous ventilation was maintained in all of their study subjects. They noted that nausea was frequently encountered in their study cohort. Thus, we expect that spontaneous ventilation will be maintained in our study subjects. Prior to the administration of ketamine, we will administer 4mg intravenous ondansetron for the pre-emptive treatment of nausea.

Research staff will be responsible for monitoring potential side effects. An experienced board-certified anesthesiologist will always monitor and care for the subject according to the standards for delivery of anesthesia at MGH. The White 5 research unit is equipped with an anesthesia machine and physiologic data are collected electronically. This research unit has been specifically designed and equipped according to MGH standards and Massachusetts regulations as an anesthetizing location, and it has been approved for this purpose by the Clinical Practices and Safety Committee of the MGH Department of Anesthesia, Critical Care and Pain Medicine. Because ketamine may cause an increase in the heart rate and blood pressure, an

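### The conscious-state cross-spectral matrix is estimated from the whole baseline recording, which includes EEG calibration movements; the awake eyes-closed part should be named instead, and the unit of the median stated

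*Combined protocol and SAP*

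**What the plan says.** Section 6 (Eigenvalue and Modal Projection Analyses) decomposes cross-spectral matrices to find the main oscillation modes in the conscious and unconscious states, then follows power in those modes over time. For each subject the conscious-state matrix is estimated "using the multitaper method using data from the full baseline period". Its counterpart uses stretches of 5 minutes or more between loss and recovery of consciousness (LOC, ROC). The matrix that is decomposed is a median, but the text does not say over what.

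Section 5 (B. Baseline) defines the recording: "A 10 to 15-minute period of EEG recording will be obtained". It has two purposes: "EEG calibration (i.e. eye movements, eye blinks, facial muscle movement) and EEG normalization (awake-eyes closed"). The minutes given to each are not stated. The same paragraph lists "end-tidal carbon dioxide, electrooculogram, electromyogram and galvanic skin response" among the physiological measurements.

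On preprocessing, Section 6 says: "We will apply an anti-aliasing filter and down-sample the EEG data to reduce computational complexity before analysis". It adds that "Bandpass filtering of the acquired signal will vary depending upon" the EEG features under study, and that stimulus events are tagged. The document nowhere sets the calibration part aside, and nowhere describes detection, rejection or correction of artefact.

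**The concern.** The baseline recording is one period with two contents, and only one of them represents quiet wakefulness. Using all of it puts eye and facial muscle activity into the matrix that stands for the conscious state. If movement forms a leading mode at some frequency, the comparison of conscious and unconscious modes partly describes movement. The modal projection over time, with its permutation procedure, takes those modes as its starting point.

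Band-pass filtering does not settle this. Muscle activity that falls inside a band of interest, such as the 30-40 Hz gamma described in Section 1, passes through the filter.

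**Working it through.** **1. The plan's own figure.** The plan gives no number for this point. Its only computed figure, n=14, reproduces with the two-sided normal approximation for two means: 2 × (1.960 + 1.282)² × (20/25)² = 2 × 10.51 × 0.64 = 13.5, rounded up to 14. No input to it uses P_baseline.

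**2. The two sections side by side.** Section 5 puts calibration movement and eyes-closed rest in one baseline recording. Section 6 uses the full period, with no artefact step. Taken together, the calibration movement is in P_baseline.

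**3. When a movement mode takes over (mean within subject).** The documents do not give the calibration share f, the level x (dB by which total power in movement windows exceeds rest) or the number k of artefact maps sharing that power. All are assumed. Set rest power to 1, and let the rest mode hold an assumed 0.61 of it. Averaging windows gives each artefact map power of about f × (10^(x/10) − 1) / k. If the maps are common to subjects, artefact leads once this exceeds about 0.61. For f = 0.2 at x = 5, 10 and 20 dB:

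- k = 1: 0.2 × 2.16 = 0.43; 0.2 × 9 = 1.80; 0.2 × 99 = 19.8.
- k = 3: 0.14; 0.60; 6.6.

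One common map therefore takes over between 5 and 10 dB. Three common maps are at the tipping point at 10 dB.

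**4. Simulation, median across subjects.** Assumed: 64 channels, 14 subjects, 150 windows each, 5 tapers, one rest mode holding 61% of rest power plus white noise, and each artefact map at cosine 0.2 with the rest mode. Windows are averaged within subject, then an element-wise median is taken across subjects; 15 runs per cell. Entries are the squared overlap of the leading eigenvector with the rest mode at 5/10/20 dB. A value of 1 means unaffected; 0.2² = 0.04 means that the leading mode is the artefact map.

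| f | One common map | Three common maps | Three maps differing by subject |
|---|---|---|---|
| 0.1 | 0.99/0.25/0.05 | 1.00/0.94/0.06 | 1.00/1.00/0.86 |
| 0.2 | 0.89/0.08/0.04 | 0.99/0.57/0.06 | 1.00/0.99/0.68 |
| 0.33 | 0.40/0.06/0.04 | 0.96/0.23/0.06 | 1.00/0.98/0.50 |
| 0.5 | 0.16/0.05/0.04 | 0.87/0.15/0.05 | 1.00/0.96/0.36 |

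With f = 0 the overlap is 1.00. The common-map columns follow the rule in step 3.

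**5. Simulation, median over windows within subject, then across subjects.** Same settings, 3 runs per cell, with x now the artefact power added on top of rest.

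| f | One common map | Three common maps | Three maps differing by subject |
|---|---|---|---|
| 0.1 and 0.2 | 1.00/1.00/1.00 | 1.00/1.00/1.00 | 1.00/1.00/1.00 |
| 0.33 | 0.99/0.98/0.97 | 1.00/1.00/1.00 | 1.00/1.00/1.00 |
| 0.5 | 0.67/0.14/0.04 | 0.99/0.98/0.06 | 1.00/1.00/1.00 |

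The change in the definition of x matters little. Under the step 5 definition, the step 4 cell for f = 0.2 and one common map is 0.56/0.08/0.04, so only the 5 dB value moves (0.2 × 3.16 = 0.63, close to 0.61). The difference between the tables comes from the unit of the median. A window median ignores a minority of loud windows; an average does not.

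**The case against.** **The wording may only be loose.** The word full may merely contrast with the partial LOC-to-ROC stretches, and Section 5 labels the movements as calibration. That is possible. But Section 5 makes the whole recording the baseline, and the word works against a narrower reading.

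**Cleaning may be intended.** Eye and muscle channels are recorded throughout, so a reader should not infer that the team will ignore artefact. What stands is that the plan states no use of those channels in cleaning the EEG.

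**The median may protect.** This is the strongest objection, and it is partly right. If the median is over windows, the problem is essentially absent up to a calibration share of one third. The across-subject reading is the more natural one, because matrices are estimated per subject and the preceding paragraph takes medians across subjects. The text still permits either.

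**The worst cases stack assumptions.** They need artefact maps shared by all subjects, a level of 10 to 20 dB, and the whole calibration share loading on the frequency analysed. Eye and muscle activity need not share a band, so the effective share at one frequency may be lower. Complete replacement of the leading mode is one end of an assumed range, not an expected result.

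**A reader might extend the point to the baseline-normalized spectrograms, the gamma comparison or the power calculation.** The documents do not support that. Section 5 ties normalization to eyes-closed data, Section 6 specifies the full period only for the cross-spectral matrices, and the power calculation takes its gamma values from Figure 2.

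**Conclusion.** The point holds at low importance. Sections 5 and 6 together admit calibration movement into P_baseline, and a less biased choice is available in the protocol's own terms.

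The size cannot be determined from the documents. It depends on the calibration share, the artefact level, how alike the artefact maps are between subjects, and the unit of the median. With an across-subject median and a 20% share, the effect runs from none (overlap 1.00) to replacement of the leading mode (0.04). With a window median first, overlap is about 1.00 for shares up to 20% and at least 0.97 at one third. It fails only near one half, and then only with maps common to subjects.

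It would go too far to say that the study's conclusions are at risk. The mode analysis is descriptive support for Aim 1. None of the six hypotheses in Section 2 is framed in terms of these modes, and the sample size does not use them.

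**What to change.** In Section 6, in the sentence containing "using the multitaper method using data from the full baseline period", replace the last four words with *the awake eyes-closed segment of the baseline period*. In the sentence on the eigenvalue decomposition, state that the median cross-spectral matrix is taken across subjects, or over windows if that is meant.

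Optionally, add that baseline and LOC-to-ROC data are screened by the same written artefact rule. Both states need it because airway support can also disturb the EEG: "These maneuvers include a jaw and chin thrust and assisted ventilation with a mask and bag as part of a circle circuit". The rule should not simply assume that the recorded electromyogram captures facial or scalp muscle, since its site is not given.

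The cost is a shorter baseline, with no new recordings. Minutes left are (1 − f) × 10 to 15, and with roughly independent windows the standard error of P_baseline is multiplied by 1/√(1 − f):

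| Assumed f | Minutes left | Factor |
|---|---|---|
| 0.2 | 8.0-12.0 | 1.12 |
| 0.33 | 6.7-10.0 | 1.22 |
| 0.5 | 5.0-7.5 | 1.41 |

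Screening, if adopted, removes further data by an unknown amount. With the 10 to 15 minutes of unresponsiveness that Section 5 expects, 1 − 5/10 = 50% to 1 − 5/15 = 67% of the LOC-to-ROC data could go before falling under the plan's 5-minute minimum.

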## 2. SPECIFIC AIMS

**AIM 1:** To use high-density EEG recordings to characterize the different brain states induced by ketamine

**Hypothesis 1.1.** Ketamine gamma-burst pattern will be associated with a zero probability of response to auditory stimuli

**Hypothesis 1.2.** Ketamine gamma-stable pattern consists of two distinct brain states: an anesthetic state with zero probability of response to auditory stimuli and a hallucinatory state with non-zero probability of response to auditory stimuli

**AIM 2:** To use high-density EEG recordings to characterize oscillatory dynamics associated with the analgesic effect of ketamine

**Hypothesis 2.1.** Ketamine theta power will correlate with analgesia

**Hypothesis 2.2.** Ketamine gamma power will not correlate with analgesia

**AIM 3:** To use inflammatory profiling of serum to understand the effect of ketamine on systemic inflammation

**Hypothesis 3.1.** Ketamine-anesthesia will be associated with decreased levels of pro-inflammatory cytokines interleukin 6 and TNF-alpha

**Hypothesis 3.2.** Levels of pro-inflammatory cytokines interleukin 6 and TNF-alpha will correlate with a decrease in perception of painful stimuli

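### Hypotheses 1.1 and 1.2 concern response probability within an EEG pattern, but Section 6 neither labels the patterns nor estimates response by pattern

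*Combined protocol and SAP*

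**What the plan says.** Section 2 (Specific Aims) conditions both Aim 1 hypotheses on an EEG pattern. Hypothesis 1.1 reads "Ketamine gamma-burst pattern will be associated with a zero probability of response to auditory stimuli". Hypothesis 1.2 begins "Ketamine gamma-stable pattern consists of two distinct brain states" and goes on to describe one state with no response and one with some response.

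Section 6 (Biostatistical Analysis) names neither pattern. What it plans is:

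- **Behavioral Analysis.** "The probability of response to verbal stimuli and the difference in probability of response will be estimated" with a Bayesian state-space model. What the difference compares is not stated. For the group analysis, "we will align the behavioral data across subjects" on LOC for induction and ROC for emergence. Then: "We will then pool the responses, and pooled data will be used to estimate group-level probabilities of response using the state-space model".
- **Spectral Analysis.** "We will compute spectrograms for all subjects using the multitaper method". Group spectrograms come from "taking the median across subjects with the data aligned to the LOC and ROC time points, respectively". Spectral differences get a 99% bootstrap interval between groups that are not named.
- **Eigenvalue and Modal Projection Analyses.** Baseline is set against one LOC-to-ROC segment, and the modal projection over time has a permutation test.
- **EEG acquisition Preprocessing.** Triggers will "tag the stimulus events for subsequent binning, temporal epoching and averaging of EEG data into the relevant evoked potential averages".

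The two patterns are described only in Section 1 (Ketamine), from 4-channel frontal EEG in 12 surgical patients. There, a slow 0.1–4 Hz rhythm alternating with 30–40 Hz bursts gave way, several minutes later, to persistent 30–40 Hz activity. The hypotheses speak of auditory and Section 6 of verbal stimuli; I take these to be the same.

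**The concern.** The quantity in the hypotheses is the probability of response given the pattern. The quantity in Section 6 is the probability of response given time from LOC or ROC. The two coincide only if every volunteer is in the same pattern at the same aligned time, which nothing in the plan establishes.

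Section 1 gives the unknown link between ketamine oscillations and loss or return of consciousness as the reason for the study. As written, Aim 1 would yield response curves and spectra on a shared time axis. It would yield no prespecified estimate of whether responses occur during gamma-burst, or of whether gamma-stable contains both unresponsive and responsive periods. If pattern boundaries are drawn later with the responses in view, they could be placed where responding stops, which would favour the zero hypothesis.

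**Working it through.** **1. The plan's own figure.** The only sample-size calculation (Section 6, Power Analysis) uses a 25 dB gamma power difference (−20 to 5 dB), SD 20 dB, alpha 0.05 and power 0.9. The two-sided normal formula for two independent means gives 2 × (20 × (1.960 + 1.282) / 25)² = 13.45, so 14, as stated. This sizes baseline against unconsciousness on gamma power. It says nothing about response by pattern.

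**2. Does any planned step deliver response given pattern?**

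| Planned step | What it gives | Why it falls short |
|---|---|---|
| State-space model | Response over time | Group version is by LOC/ROC time; no split by pattern |
| Difference in response probability | A contrast | Comparison not named |
| Subject spectrograms | Power by time and frequency | No rule for amplitude, duration or channel to turn power into a label |
| Bootstrap and permutation inference | Formal inference on EEG power | Response does not enter |
| Stimulus triggers | Stimulus times in the EEG record | Stated use is evoked potentials |

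**3. Can LOC-to-ROC stand in for a pattern?** No, for two reasons. Section 5C uses the button presses to resolve loss and recovery, and no LOC/ROC rule is given. Low response inside the window is therefore partly built in, and a cut of gamma-stable at ROC would likewise produce an unresponsive and a responsive part largely by construction. The window may also hold both patterns: Section 1 puts the switch at several minutes, and Section 5C expects 10–15 minutes of unresponsiveness.

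**4. What the pooled curve can say about Hypothesis 1.1.** Suppose k of 15 volunteers are in gamma-burst at an aligned time, each contributing equally. Response within gamma-burst is then at most the pooled probability ÷ (k/15). The values of k are assumptions.

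| Pooled probability | k = 2 | k = 6 | k = 12 |
|---|---|---|---|
| 0% | 0% | 0% | 0% |
| 1% | 7.5% | 2.5% | 1.25% |
| 2% | 15% | 5% | 2.5% |

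A near-zero curve is therefore informative, but only once k is known, and k requires labels.

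**5. Away from zero, as in Hypothesis 1.2 and the transitions.** Assume 6 of 15 volunteers are in gamma-stable and the pooled response is 36%. Three different truths fit:

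- 0% in the six and 60% in the rest: (6×0 + 9×0.60)/15 = 0.36
- 36% in all: (6×0.36 + 9×0.36)/15 = 0.36
- 90% in the six and 0% in the rest: (6×0.90 + 9×0)/15 = 0.36

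If spectra depend only on the pattern, the group spectrogram is also the same in all three.

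**6. Pooling caveat.** Section 6 states no subject-level term for the pooled fit. To see whether this could matter, assume 5 minutes in a pattern at a mean interval of 6 s (the plan says 4 to 8 s). That is 50 stimuli each, 15 × 50 = 750 in all. With no response at all, the 95% upper bound is 1 − 0.05^(1/750) = 0.40% if stimuli are independent. An exact beta-binomial with an assumed intraclass correlation (ICC) of 0.01, 0.05, 0.10 or 0.20 gives 0.49%, 0.80%, 1.15% or 1.83%. The documents give no ICC, and this is not the planned state-space model, so these figures show direction only.

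**7. How firm can a zero verdict be?** For the same 750 stimuli with no response, I computed the 95% upper credible limit of the mean under a beta-binomial. The six priors combined a Jeffreys or uniform prior for the mean with an ICC uniform on 0–0.3, 0–0.5 or 0–1. The limit ran from 1.1% to 10.4%. The verdict depends heavily on the prior, so the prior has to be fixed beforehand.

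**The case against.** The strongest reply has four parts.

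- **The data allow the analysis.** EEG is continuous, stimuli are frequent and trigger-tagged, and a spectrogram is planned for every subject. This stands. A reader might infer that the trial cannot answer Aim 1; the documents do not support that, because only the written analysis is missing.
- **The pooled curve is not silent on Hypothesis 1.1.** Section 1 places the burst pattern right after induction, when few responses are expected, and near zero the pooled curve bounds response in gamma-burst. This also stands, subject to the unknown share and to LOC being located from the same presses.
- **The planned inference is more than visual.** The bootstrap intervals and the permutation test are formal procedures. True, but they concern EEG power.
- **Pooling need not be wrong.** A reader might infer that the plan treats the stimulus as the unit and that its group interval is too narrow. Section 6 gives neither the observation model nor an ICC, and it does not exclude separate fits per subject. If every volunteer's probability is truly zero, as Hypothesis 1.1 says, pooling loses nothing. Only a conditional caveat survives.

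None of this supplies a labelling rule or an estimate of response by pattern.

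**Conclusion.** The concern holds as a mismatch between hypotheses and analysis, and it should be fixed before the data are analysed. Confidence is high: it rests on reading Sections 1, 2, 5C and 6 together and needs no assumed number. Hypothesis 1.2 is not testable under the written plan, because gamma-stable is never isolated. Hypothesis 1.1 can at most be bounded, by a factor of 1/share that is unknown without labels (2.5 at an assumed 6 of 15). It also has no stated numerical meaning of zero. The shares and percentages in the illustrations are assumptions. Whether the pooled interval is too narrow, and by how much, cannot be determined from the documents.

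**What to change.** (a) Before analysis, write an EEG-only labelling rule with band, amplitude, duration and channel criteria, starting from the Section 1 bands and applied blind to responses. Those bands come from frontal recordings in surgical patients, so the remaining criteria must be set for the 64-channel montage. Label each trigger-tagged stimulus as baseline, gamma-burst, gamma-stable or other, and estimate response probability by label.

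(b) Within gamma-stable, model response over time for each subject. Prespecify how a zero and a non-zero state would be shown, for example by comparing a one-state with a two-state model, rather than by cutting at ROC.

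(c) Put a subject-level effect in the by-pattern model and report how many subjects gave any response in each pattern. Keep the pooled LOC/ROC-aligned curves as description, with the LOC/ROC rule stated. Say what the difference in response probability compares.

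(d) Judge zero by an upper 95% limit against a small value chosen in advance, with the prior fixed and a sensitivity analysis over priors.

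Cost: the effort of blind labelling, wider intervals than a pooled fit, and a conclusion about zero that remains sensitive to the prior. No new data, visits or procedures are needed.
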